15.3 Deaths, Other Serious Adverse Events, and Other Significant Adverse Events

15.3.1 Deaths

Population: SAF analysis set

All deaths, deaths within 60 days after first dose of trial treatment, and deaths within 30 days and within 90 days after last dose of trial treatment, as well as reasons for deaths (disease progression, adverse event related to study treatment, adverse event not related to study treatment, other, unknown), will be tabulated based on all relevant information available in the eCRF:

- Number of deaths

- Number of deaths within 60 days after first dose of trial treatment
- Number of deaths within 30 days after last dose of trial treatment
- Number of deaths within 90 days after last dose of trial treatment
- Primary reason of death

In addition, the date (non-imputed) and cause of death will be provided in individual subject data listings together with selected dosing information (date of first/last administration of peposertib, RT and capecitabine, dose level and number of fraction days/duration).

Subject listing of deaths includes columns for:

- Subject identification
- Age
- Sex
- Race
- AEs with fatal outcome (list PTs of AEs with outcome=fatal),
- Flag for death within 60 days after first dose of peposertib
- Flag for death within 60 days after first dose of RT
- Flag for death within 60 days after first dose of capecitabine
- Flags for death within 30, 90 days after last dose of peposertib
- Flags for death within 30, 90 days after last dose of RT
- Flags for death within 30, 90 days after last dose of capecitabine

Finally, all treatment related TEAEs (i.e. peposertib, RT or capecitabine) leading to death, will be listed in a separate listing, displaying:

- Dose level
- Subject identification number
- Age
- Sex
- Race
- First and last dose date for peposertib, RT and capecitabine
- Reported Term with SOC and PT
- Start and end date with their corresponding treatment day
- Treatment Emergent Adverse Events flag (N/Y)

- Timing related to treatment (if same day of treatment administration)
- TEAE related to peposertib flag (N/Y)
- TEAE related to RT flag (N/Y)
- TEAE related to capecitabine flag (N/Y)
- Serious Adverse Events flag (N/Y)
- DLT flag (Y/N)
- CTCAE Grade
- Action taken with peposertib, with RT and with capecitabine
- Outcome of AE
- Date of death with the corresponding treatment day

15.3.2 Serious Adverse Events

Population: SAF analysis set

SAEs will be summarized for each dose level and overall, by SOC, and PT in alphabetical order (please refer to Section 15.2.1 for items to be listed).

In addition, subject listings of SAEs will be provided.

15.4 Clinical Laboratory Evaluation

Population: SAF analysis set

Listings and summaries by visit will include all assessments, whereas shift tables and summaries of worst on-treatment values will not consider assessments after the on-treatment period.

Local laboratory values (including corresponding normal ranges) will be presented in summary statistics, shift tables and boxplots. In addition, liver toxicity will be assessed with Hy's Law analysis.

Laboratory results will be classified according to the NCI-CTCAE version 5.0. Additional laboratory results that are not part of NCI-CTCAE will be presented according to the categories: below normal limits, within normal limits and above normal limits (according to the laboratory normal ranges).

Common Terminology Criteria (CTC) gradable parameters

In this trial, Common Terminology Criteria (CTC) gradable parameters are the following:

Table 11 Common Terminology Criteria (CTC) gradable parameters

Category	Parameter (LBTEST)	Parameter code (LBTESTCD)	Name in NCI-CTC version 5.0	Direction of abnormality
Clinical Chemistry				
Electrolytes	Calcium	CA	Hypocalcemia/Hypercalcemia	Low/High
Electrolytes	Magnesium	MG	Hypomagnesemia/Hypermagnesemia	Low/High
Electrolytes	Potassium	K	Hypokalemia/Hyperkalemia	Low/High
Electrolytes	Sodium	SODIUM	Hyponatremia/Hypernatremia	Low/High
Enzymes/cardial	Creatine phosphokinase (CPK)	CK	CPK increased	High
Enzymes/liver	Alanine aminotransferase	ALT	Alanine aminotransferase increased	High
Enzymes/liver	Alkaline phosphatase	ALP	Alkaline phosphatase increased	High
Enzymes/liver	Aspartate aminotransferase	AST	Aspartate aminotransferase increased	High
Enzymes/liver	Total bilirubin	TBILI	Blood bilirubin increased	High
Metabolism	Glucose	GLUC	Hypoglycemia	Low
Metabolism	Uric acid ⁽¹⁾	URATE	Hyperuricemia	High
Plasma proteins	Albumin	ALB	Hypoalbuminemia	Low
Renal/kidney	Creatinine	CREAT	Creatinine increased	High
Renal/kidney	Creatinine clearance	CREATCLR	Chronic kidney disease	Low
Enzymes/cardial	Lactate dehydrogenase	LDH	Lactate dehydrogenase increased	High
Coagulation	Activated partial thromboplastin time	APTT	Activated partial thromboplastin time prolonged	High
Coagulation	International normalized ratio (INR)	INR	INR increased	High

Category	Parameter (LBTEST)	Parameter code (LBTESTCD)	Name in NCI-CTC version 5.0	Direction of abnormality
Hematology				
Platelets	Platelets count	PLAT	Platelet count decreased	Low
Red blood cells	Hemoglobin	HGB	Anemia/Hemoglobin increased	Low/High
White blood cells/differential	White blood cell count	WBC	White blood cell decreased/Leukocytosis	Low/High
White blood cells/differential	Absolute lymphocytes count	LYM	Lymphocyte count decreased/increased	Low/High
White blood cells/differential	Absolute neutrophils count	NEUT	Neutrophil count decreased	Low/High
White blood cells/differential	Eosinophils	EOS	Eosinophilia	High

(1) According to CTCAE grade, if uric acid value is greater than ULN it should be graded as follows:

o Grade 1 >ULN without physiologic consequences

o Grade 3 >ULN with physiologic consequences

As information on physiologic consequences of laboratory parameters are not available, values > ULN will all be graded as Grade 1 (if any physiologic consequences are observed, it should be completed as an adverse event).

For all CTC gradable parameters, shift tables from baseline to worst grade on-treatment will be produced. For those parameters which are graded with two directions of toxicities such as potassium (hypokalemia/hyperkalemia), the toxicities will be summarized separately. Low direction toxicity (e.g., hypokalemia) grades at baseline and on-treatment will be set to 0 when the variables are derived for summarizing high direction toxicity (e.g., hyperkalemia), and vice versa.

Non-CTC gradable parameters

In this trial, non-CTC gradable parameters are displayed in table below

Table 12 Non-CTC gradable parameters

Category	Parameter (LBTEST)	Parameter code (LBTESTCD)	Direction of abnormality
Clinical chemistry			
Electrolytes	Phosphorus (phosphate)	PHOS	Low/High
Electrolytes	Chloride	CHLO	Low/High
Plasma proteins	Total protein	PROT	Low
Hematology			
Red blood cells	Hematocrit	HCT	High/Low
Red blood cells	Mean corpuscular hemoglobin	MCH	High/Low
Red blood cells	Mean corpuscular volume	MCV	High/Low
Red blood cells	Reticulocytes	RETI	High/Low
White blood cells/differential	Basophils	BASOLE	High
White blood cells/differential	Monocytes	MONOLE	High/Low

Direct bilirubin (DBIL), Blood urea nitrogen (BUN) and Red blood cells (RBC) parameters will only be presented in listings

Shift tables based on the normal range from baseline to lowest and highest on-treatment value will be produced with the following categories for all hematology and blood chemistry parameters (CTC gradable and non-CTC gradable):

- Baseline: Low/Normal/Missing/Overall for low parameters;
Normal/High/Missing/Overall for high parameters
- Lowest On treatment: Low/Normal/Missing/Overall
- Highest On trial: Normal/High/Missing/Overall
- Normal category includes low values for high parameters and high values for low parameters.

Boxplots will be produced for all quantitative hematology and biochemistry parameters, to display:

- Values by time point
- Difference from baseline to highest deviation on treatment by cohort

All CTC gradable and non-CTC gradable parameters will be listed for each measurement (pre treatment, on treatment and post treatment). Parameters will be grouped by category.

Listings will include at least the following items:

- Dose level
- Subject identification number
- First / last dosing date for peponsertib, RT and capecitabine
- Parameters
- Visit
- Date (Treatment day)
- Analysis value
- SI unit
- Change from baseline
- Reference range status (Low, Normal, High)
- CTC grade (with associated CTC name)
- Baseline flag (Yes/No)
- Worst value on-treatment flag (Yes/No)
- On treatment flag (pre/on/post)

Gradable parameters with at least one value with Grade ≥ 3 , will be considered clinically significant laboratory values. For hematology and biochemistry, a listing displaying clinically significant laboratory values will be provided. For each participant, only parameters where at least one value has Grade ≥ 3 will be displayed (all visits for the corresponding parameter will be displayed). The listing will be sorted by dose level, subject ID, parameter name, and datetime.

Coagulation parameters

All coagulation parameters will be listed for each measurement (pre treatment, on treatment and post treatment).

Urinalysis

A listing of urinalysis and microscopic analysis will be provided.

Liver toxicity

On-treatment liver function tests will be summarized in a table presenting the number and percentage of participants, by dose level and overall:

- ALT $\geq 3 \times$ ULN, ALT $\geq 5 \times$ ULN, ALT $\geq 10 \times$ ULN, ALT $\geq 20 \times$ ULN
- AST $\geq 3 \times$ ULN, AST $\geq 5 \times$ ULN, AST $\geq 10 \times$ ULN, AST $\geq 20 \times$ ULN
- Total Bilirubin $\geq 2 \times$ ULN
- (ALT or AST) $\geq 3 \times$ ULN and Total Bilirubin $\geq 2 \times$ ULN (Hy's Law case)

Categories will be cumulative, i.e., a participant with an elevation of AST $\geq 10 \times$ ULN will also appear in the categories $\geq 5 \times$ ULN and $\geq 3 \times$ ULN.

An evaluation of Drug-Induced Serious Hepatotoxicity (eDISH) plot will also be created by graphically displaying:

- peak serum ALT(/ULN) vs simultaneous Total Bilirubin (/ULN) including reference lines at ALT > 3 ULN and bilirubin > 2 ULN.
- peak serum AST(/ULN) vs simultaneous Total Bilirubin (/ULN) including reference lines at AST > 3 ULN and bilirubin > 2 ULN.

Participants under the Hy law's case (right upper corner) will be flagged with their subject identifier.

In addition, a listing of all TBILI, ALT, AST and ALP values for subjects with an on-treatment TBILI $\geq 2 \times$ ULN, ALT $\geq 3 \times$ ULN or AST $\geq 3 \times$ ULN will be provided.

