In conclusion, emerging clinical safety data from studies EMR100036-001 and EMR100036-002, and supportive results of a comprehensive series of nonclinical safety pharmacology, PK, and toxicology studies, as well as primary and secondary PD findings support continued clinical development of peposertib in combination with RT, and/or chemotherapy.

3 Objectives and Endpoints

Study objectives and endpoints are provided in [Table 6](#). Statistical analysis of the endpoints is described in [Section 9.4](#).

Table 6 Study Objectives and Endpoints

Objectives	Endpoints (Outcome Measures)	Endpoints (Outcome Measures) Timeframe
Primary		
To define an MTD and RP2D of peposertib in combination with capecitabine and RT	Occurrence of dose limiting toxicities	Time from first study intervention to the end of CRT with a final assessment at 4 weeks after surgery
Secondary		
To evaluate safety and tolerability of peposertib in combination with capecitabine and RT	
 • Occurrence of TEAEs and treatment-related adverse events according to the NCI-CTCAE version 5.0 • Occurrence of abnormalities (Grade ≥ 3) in laboratory test values, markedly abnormal vital sign measurements, and clinically significantly abnormal ECGs including clinically important increases in QT interval (QTcF) 	Time from first study intervention to final assessment at 1 year
To explore antitumor activity of peposertib in combination with capecitabine and RT	
 • Composite endpoint of pCR/cCR • Disease-free Survival • pCR • cCR • Local recurrence and/or distant metastasis • Neoadjuvant rectal score 	
 • Pathology evaluation of specimen after surgery (pCR) and clinical evaluation 1 to 2 weeks prior to surgery (cCR) • Time from first study intervention to final assessment at 1 year • Pathology evaluation of specimen after surgery • Time from first study Intervention until clinical evaluation 1 to 2 weeks prior to surgery • Time from surgery to final assessment at 1 year • Pathology evaluation of specimen after surgery
To assess the PK of peposertib	PK profile of peposertib in terms of PK parameter estimates (e.g. C _{max} , AUC _{0-t} , t _{max} , CL/f, Vz/f, t _{1/2})	FD1 and FD9

CCI

cCR=Clinical Complete Response, CRT=chemoradiotherapy, CCI [REDACTED]
[REDACTED] ECG=electrocardiogram, FD=fraction day, MTD=maximum tolerated dose, NCI-CTCAE=National Cancer

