9.4.2 Safety Analyses

Statistical analysis methods for safety endpoints are described in [Table 13](#).

Table 13 Statistical Analysis Methods for Safety Endpoints

Endpoint	Statistical Analysis Methods
Primary	
Occurrence of DLTs	The number and proportion of participants experiencing a DLT confirmed by the SMC during the DLT period will be reported by dose level. Analysis will be based on the DE Analysis Set.
Secondary	
Occurrence of TEAEs and treatment-related AEs according to the CTCAE version 5.0	All AEs will be coded according to the MedDRA, version 21.0 or higher. The severity of AEs will be graded using NCI-CTCAE v5.0 toxicity grades. Adverse events related to study intervention will be defined as any AE considered related to any study intervention. In addition, missing classifications concerning study intervention relationships will be considered related to the study intervention(s). Adverse events observed from the first dose until 30 days after last study intervention administration (i.e. TEAEs) will be summarized according to MedDRA system organ classes and preferred terms. The incidence and type of the following will be analyzed: 
 • TEAEs and SAEs • TEAEs and SAEs related to study intervention • TEAEs with NCI-CTCAE Grades ≥ 3 • TEAEs related to study intervention with NCI-CTCAE Grades ≥ 3 • AEs leading to withdrawal, dose modifications, or permanent study intervention discontinuation • Deaths and reasons for death will be tabulated. In addition, deaths within 30 days from last dose administration and deaths beyond this period up to 90 days follow-up and reasons for death will be tabulated. Analyses will be based on the Safety Analysis Set.

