Occurrence of abnormalities (Grade ≥ 3) in laboratory test values and markedly abnormal vital sign measurements, and clinically significantly abnormal ECGs including clinically important increases in QT interval (QTcF)	Laboratory results will be classified by grade according to NCI-CTCAE v5.0. The worst on-study grades after the first study intervention will be summarized. Shifts in toxicity grades from first treatment to highest grade will be displayed. Results for variables that are not part of NCI-CTCAE will be presented as below, within, or above normal limits. Only participants with postbaseline laboratory values will be included in these analyses. Physical examination, including vital signs (body temperature, respiratory rate, pulse rate, and blood pressure), and 12-lead ECG, recorded at baseline and after administration of study intervention. Analyses will be based on the Safety Analysis Set.

AE=adverse event, DLT=dose limiting toxicity, ECG=electrocardiogram, MedDRA=Medical Dictionary for Regulatory Activities, NCI-CTCAE=National Cancer Institute Common Terminology Criteria of Adverse Events, SAE=serious adverse event, SMC=Safety Monitoring Committee, TEAE=treatment-emergent adverse event.

Analyses for SMC Meetings:

During dose escalation the analysis will focus on safety and available PK data.

The Bayesian escalation approach will be applied to assist the SMC in the choice of the next dose level. The SMC will receive results of a Bayesian 2-parameter dose-toxicity model with overdose control, updated with the observed DLT data. The recommended next dose level will minimize the Bayesian Risk among all considered dose levels, while at the same time limiting the risk of overdose or excessive toxicity (Neuenschwander 2008). The target toxicity is 30%. Details of the model including the prior distribution and toxicity regions are described in [Appendix 10](#).

The following peposertib dose levels will be considered for escalation decisions: 30, 50, 100, 200, 400, 600, and 800 mg; 50 mg is the starting dose. Dose increases will not exceed 100% of the highest dose level considered safe at the time of escalation decision. The SMC may decide to deviate from the suggestion of the Bayesian escalation approach. Also, the SMC may decide to change the dosing regimen. In such a case the model will be extended, or a separate model will be set up.

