Percent change from baseline: $100 * (visit value - baseline value) / baseline value$

Definition of on treatment period:

On treatment period is defined as the time from the first administration of study intervention to the last administration of study treatment + 30 days, or the clinical cut-off date (if the treatment is still ongoing), or death, whichever occurs first.

Date of last known to be alive

The date of last known to be alive will be derived for participants not known to be dead at the analysis cut-off using the latest complete date among the following:

- All subject assessment dates:

- Laboratory assessments using information from “Hematology”, “Biochemistry”, “Coagulation”, “Urinalysis”, “Pregnancy test” and “Creatinine Clearance” eCRF pages (LBDTC variable from LB SDTM domain to be used)
- Vital signs using information from “Vital signs” eCRF page (VSDTC variable from VS SDTM domain to be used)
- Performance status using “ECOG Performance status” eCRF page (QSDTC variable from QS SDTM domain to be used)
- ECG, using information from both local and central ECGS (EGDTC variable from EG SDTM domain to be used)
- Tumor assessments using “Tumor assessments” eCRF pages (TRDTC/TUDTC variable from TR/TU SDTM domain to be used)
- Surgery information using “Rectal Surgery at week 15”, “Rectal Surgery after Week 15”, “Surgery after discontinuation” eCRF pages
- Anti-cancer treatment after discontinuation start and end date from “Anti-Cancer treatment after discontinuation” eCRF page.
- Start dates of concomitant medications or anti-cancer therapies administered after study treatment termination using “Concomitant medications”, “Anti-cancer treatment after discontinuation details” eCRF pages (CMSTDTC variable from CM SDTM domain to be used)
- AE start dates from “Adverse events details” eCRF page (AESTDTC variable from AE SDTM domain to be used)
- Study treatment administration dates using “M3814 (PEPOSERTIB)/PLACEBO Administration Details”, “RT Administration” and “Capecitabine Administration” eCRF pages (EXSTDTC variable from EX SDTM domain to be used)
- Last known to be alive date using “Survival Follow-up page” (SSDTC variable from SS SDTM domain where SSCAT=“SURVIVAL FOLLOW-UP”), where status is “Alive”.

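### SAP 15.4 ends worst laboratory grades at last dose + 30 days, so no planned table counts participants by worst grade over the 1-year laboratory endpoint period

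*SAP*

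**What the plan says.** **Protocol.** Section 3 (Table 6) and the Synopsis make the occurrence of Grade 3 or higher laboratory abnormalities a secondary safety endpoint, with the timeframe "Time from first study intervention to final assessment at 1 year". Section 9.4.2 (Table 13) gives the method: "The worst on-study grades after the first study intervention will be summarized", and "Shifts in toxicity grades from first treatment to highest grade will be displayed". Neither sentence sets an end-of-treatment limit. The same table does use a 30-day limit, but in the adverse event row, where it defines treatment-emergent events: "Adverse events observed from the first dose until 30 days after last study intervention administration".

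**SAP.** Section 15.4 says that "shift tables and summaries of worst on-treatment values will not consider assessments after the on-treatment period", and for CTC-gradable parameters that "shift tables from baseline to worst grade on-treatment will be produced". Section 9 defines the on-treatment period as "the time from the first administration of study intervention to the last administration of study treatment + 30 days", or to the data cut-off (if treatment is ongoing) or death if earlier. Section 7, which lists changes from the protocol's planned analyses, does not mention this restriction.

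Two further inconsistencies lie in the SAP itself. The objectives table in Section 5 still runs this endpoint to 5 years. In the normal-range shift table of 15.4, the lowest value is labelled on treatment and the highest on trial.

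**The concern.** The protocol's on-study wording and the SAP's on-treatment wording describe different windows. If the SAP is followed, the tabulated Grade 3 or higher laboratory incidence will stop before surgery, although the endpoint it serves is defined to 1 year. A reader of the study report would not learn from SAP Section 7 that the window had been shortened.

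Timing adds to this. The primary analysis is triggered at the end of short-term follow-up, about Week 19. Participants who completed treatment have left the on-treatment window by then. The later 1-year analysis can add no new laboratory value for them to the worst-grade or shift tables.

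**Working it through.** The documents give no figure to reproduce here, so the check is a calendar count followed by a comparison of outputs.

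**Inputs.** Treatment is 25 or 28 fraction days (FD), 5 per week (protocol Synopsis). The total permitted radiotherapy delay is at most 7 days (protocol 6.6.3.4). The window extends "to the last administration of study treatment + 30 days" (SAP Section 9). Visits and visit windows come from protocol Tables 1 and 2.

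**Step 1: end of the on-treatment window.** End day = day of last FD + delay + 30. The ranges reflect the weekday on which FD1 falls.

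| Schedule | Delay (days) | Last dose (day) | Window ends (day) | Share of 365 days |
|---|---|---|---|---|
| 25 FD | 0 | 33–35 | 63–65 | 17.3–17.8% |
| 25 FD | 7 | 40–42 | 70–72 | 19.2–19.7% |
| 28 FD | 0 | 38–40 | 68–70 | 18.6–19.2% |
| 28 FD | 7 | 45–47 | 75–77 | 20.5–21.1% |

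The days left out number 365 − 77 = 288 to 365 − 63 = 302.

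**Step 2: earliest day of each later laboratory visit.** Earliest day = 7 × (week − 1) + 1 − visit window in days.

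- Week 14: 91 + 1 − 7 = 85
- Week 19: 126 + 1 − 14 = 113
- Week 21: 140 + 1 − 7 = 134
- Week 27: 182 + 1 − 14 = 169
- Week 39: 266 + 1 − 14 = 253
- Week 52: 357 + 1 − 14 = 344

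All six lie beyond day 77. For the earliest possible Week 14 visit to count, the last dose would have to fall on day 85 − 30 = 55 or later, which is 8 days after the latest day in Step 1.

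**Step 3: share of scheduled data.** Fixed hematology and chemistry visits in the treatment period are FD1, 6, 11, 16, 21 and 25/28, so six fall inside the window and six after it (6/12 = 50%). If the FD1 sample serves as baseline, which its −3-day window allows, the share is 5/11 = 45%. Optional weekly toxicity visits from Week 7 can add some values inside the window.

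**Step 4: which planned outputs cover the later values.**

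- *Shift tables by worst CTC grade and the liver function counts (SAP 15.4):* on-treatment only.
- *By-visit summaries and boxplots by time point:* all assessments, but per visit, not worst grade per participant. SAP Section 9 also shows a visit only if all subsequent visits have 3 or more participants. It does not say whether this applies by dose level; planned cohorts are of 3.
- *Listing of Grade 3 or higher hematology and biochemistry (SAP 15.4):* by participant, all visits, no on-treatment limit stated, but no counts.
- *Late-toxicity table (SAP 15.2.3):* counts by worst grade, but adverse events only.

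None of these counts participants by worst laboratory grade from first dose to 1 year.

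**The case against.** **Nothing is lost.** A reader might infer that late Grade 3 or higher values go unreported. They do not: the listing in SAP 15.4 shows them by participant, and the laboratory listings carry a pre/on/post-treatment flag. With 19 participants treated by 06 May 2021 and enrollment closed, someone could count by hand. This stands, and it limits the point to a missing table.

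**Late toxicity has its own table.** A reader might also infer that the purpose of the 1-year follow-up is defeated. The documents do not support that. The late radiotherapy toxicities named in protocol 2.3 are clinical (mucositis, fibrosis, bowel perforation), and SAP 15.2.3 tabulates adverse events starting after the on-treatment period by worst grade. It does not replace a laboratory count, though. Under Appendix 7 an abnormal value becomes an adverse event only if it is symptomatic, leads to discontinuation or is judged medically important. Under 8.3.1, unrelated non-serious events are not recorded after short-term follow-up.

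**The 1-year timeframe need not bind every table.** The same Table 6 cell covers treatment-emergent adverse events, which the protocol itself ends 30 days after the last dose. This weakens an argument from the timeframe alone. But Table 13 writes the 30-day limit for adverse events and says on-study for laboratory grades, and the narrowing is not declared.

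**The restriction is defensible.** After Week 15, values mix in surgery and permitted adjuvant chemotherapy, there is no comparator, and the study is exploratory. That is a sound reason to keep the on-treatment tables and separate the later period. It is not a reason to leave the later period without a count.

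**Conclusion.** The mismatch is real. The protocol specifies worst on-study grade for an endpoint running to 1 year. The SAP's worst-grade and shift tables stop at about day 63 to 70 (up to about day 77 with the maximum delay), and Section 7 is silent.

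The window is 17 to 21% of the year by calendar time. A reader might take that to mean that only a fifth of the laboratory data is used. It does not, because about half of the fixed hematology and chemistry visits fall inside it. For participants who complete treatment, the other half enters no worst-grade table.

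The consequence is a reporting gap, not loss of data or of late-toxicity reporting, and it does not touch the primary endpoint. It is worth closing because otherwise no table reports this secondary endpoint over its stated period.

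The calendar figures assume five fractions a week without holidays, delay within the permitted 7 days, and visits within their windows.

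**What to change.** 1. Keep the on-treatment shift and worst-value tables. Add to SAP 15.4 one table of participants by worst CTCAE grade, including Grade 3 or higher, by dose level and overall, from first dose to the 1-year assessment. Split it into on-treatment and after on-treatment to Week 52, with a footnote that later values include the effects of surgery and adjuvant chemotherapy. Give the number of participants with a value in each period as the denominator.
2. State in SAP Section 7 that the shift tables remain restricted to the on-treatment period, unlike protocol Table 13.
3. Correct the 5-year timeframe in SAP Section 5 to the protocol's 1 year.
4. Reconcile the on-treatment and on-trial labels in the normal-range shift table.

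The cost is a short SAP revision and one additional table. The values are already collected and graded, and the pre/on/post flag already exists, so no new data are needed. The drawback is that the later column cannot be attributed to study treatment alone, which is why it stays separate.

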6.6.1 Definition of Dose Limiting Toxicity

A DLT is defined as any of the following TEAEs considered possibly related to peposertib and/or capecitabine and/or RT by the Investigator and/or the Sponsor up to completion of the assigned CRT treatment (25 FD or 28 FD) (DLT period). A DLT must be confirmed by the SMC:

1. An adverse drug reaction that, in the opinion of the SMC, is of potential clinical significance such that further dose escalation would expose participants to unacceptable risk
2. Any occurrence of drug-induced liver injury (DILI) meeting the Hy's law criteria (i.e. defined as aminotransferases $> 3 \times$ ULN, alkaline phosphatase $< 2 \times$ ULN, total bilirubin $\geq 2 \times$ ULN, with no other reason to account for these abnormalities)
3. Any Grade 3 toxicity, excluding:
 - a) Diarrhea (< 7 days duration) despite early, adequate and optimal antidiarrhea therapy
 - b) Neutropenia lasting for ≤ 5 days and not associated with fever

- c) Isolated Grade 3 lymphocytopenia without clinical correlate
 - d) Grade 3 radiation dermatitis that resolves to Grade ≤ 2 with supportive measures within 5 weeks
 - e) Nausea and vomiting (< 3 days duration) with adequate and optimal therapy
 - f) Fatigue or headache (< 7 days duration) following initiation of adequate supportive care
 - g) Any other single laboratory values out of the normal range that have no clinical significance as confirmed by the Investigator, and that resolve to Grade 2 or less with adequate measures within 7 days
 - h) Grade 3 thrombocytopenia without bleeding
4. All Grade ≥ 4 AEs at least possibly related to study intervention, irrespective of duration, excluding:
- a) Isolated Grade 4 lymphocytopenia without clinical symptoms
 - b) Neutropenia lasting for ≤ 5 days and not associated with fever
5. Any toxicity related to study intervention that causes the participant to receive less than 80% of the planned peposertib, capecitabine or RT dose

[figure not shown]

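### The SAP's Hy's Law count and eDISH flags omit the protocol's alkaline phosphatase limit and use cut-offs that match neither the protocol nor each other

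*SAP*

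**What the plan says.** Protocol 6.6.1 makes the following a DLT (criterion 2): "Any occurrence of drug-induced liver injury (DILI) meeting the Hy's law criteria". It spells the criteria out as "aminotransferases $> 3 \times$ ULN, alkaline phosphatase $< 2 \times$ ULN, total bilirubin $\geq 2 \times$ ULN, with no other reason to account for these abnormalities". The window runs "up to completion of the assigned CRT treatment (25 FD or 28 FD) (DLT period". No interval between the aminotransferase and bilirubin values is given.

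SAP 15.4 (Liver toxicity) plans two summaries on the safety analysis set.

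- **Table.** "On-treatment liver function tests will be summarized in a table presenting the number and percentage of participants, by dose level and overall". Its last row reads "ALT or AST) $\geq 3 \times$ ULN and Total Bilirubin $\geq 2 \times$ ULN (Hy's Law case". There is no ALP limit, no exclusion of other causes, and no statement on whether the two values must come from the same sample.
- **eDISH plots.** One plot shows "peak serum ALT(/ULN) vs simultaneous Total Bilirubin (/ULN) including reference lines at ALT > 3 ULN and bilirubin > 2 ULN". A second does the same for AST. Participants in the corner labelled as Hy's law ("right upper corner) will be flagged with their subject identifier") are identified individually. ALP does not enter.

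The on-treatment period in SAP section 9 is "the time from the first administration of study intervention to the last administration of study treatment + 30 days", or to cut-off or death if earlier. SAP 15.4 also plans a listing of all bilirubin, ALT, AST and ALP values for anyone who passes any one of the bilirubin, ALT or AST thresholds.

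**The concern.** Three different rules carry the name Hy's law, and SAP section 7, which records changes from the protocol's planned analyses, does not mention the difference. Raised liver enzymes are among the important potential risks in protocol 2.3, so readers of the study report are likely to take a Hy's Law count or flag at face value.

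Two kinds of error follow. First, ALP is what separates hepatocellular from cholestatic injury in the protocol's own wording (6.6.1, and the hepatocellular row of Table 10). Inclusion criterion 8 admits ALP up to 3 × ULN, so a participant can enter the study already above the protocol's limit of 2 × ULN. While ALP stays there, that participant cannot meet the protocol criterion, yet can be counted and flagged by the SAP. Second, chemistry is drawn weekly during treatment (protocol Table 1), and each plot uses bilirubin only at the aminotransferase peak. A bilirubin rise one sample later is not plotted, even if ALT is still above 3 × ULN on that day.

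**Working it through.** The plan states no figure to reproduce. The check sets the rules side by side and applies them to example profiles.

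**Rules (all in × ULN)**

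| | Protocol 6.6.1 | SAP table | SAP eDISH |
|---|---|---|---|
| ALT or AST | > 3 | ≥ 3 | > 3, at its peak |
| Total bilirubin | ≥ 2 | ≥ 2 | > 2, at that peak |
| ALP | < 2 | none | none |
| Other cause excluded | yes | no | no |
| Pairing of values | not stated | not stated | same time as peak |
| Window | to end of chemoradiotherapy | to last dose + 30 days | not stated separately |

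The table differs from the protocol on the aminotransferase cut-off, the plot differs on bilirubin, and the two SAP outputs differ from each other on both.

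**Logical tests.** Protocol laboratory limits: any sample with max(ALT, AST) > 3, bilirubin ≥ 2 and ALP < 2. Table: ALT or AST ≥ 3 and bilirubin ≥ 2. eDISH: at the sample with peak ALT, ALT > 3 and bilirubin > 2; or the same at peak AST.

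**Profiles.** The values are illustrative assumptions, not trial data.

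| Profile | ALT / AST / bilirubin / ALP | Protocol limits | Table | eDISH flag |
|---|---|---|---|---|
| A, bilirubin on the boundary | 5 / 4 / 2.0 / 1.2 | yes | yes | no |
| B, ALT on the boundary | 3.0 / 2.5 / 2.5 / 1.2 | no | yes | no |
| C, bilirubin lags | day 15: 8 / 6 / 1.2 / 1.1; day 22: 4 / 3.5 / 2.6 / 1.3 | yes (day 22) | yes | no |
| D, cholestatic | 5 / 4 / 3 / 4.0 | no | yes | yes |
| E, four weeks apart | day 8: 4 / 3.5 / 1.0 / 1.0; day 36: 1.2 / 1.0 / 2.3 / 1.2 | depends on pairing | depends on pairing | no |
| F, plain case | 6 / 5 / 3 / 1.2 | yes | yes | yes |

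The rules disagree in A to D. In C, the plotted points are (8, 1.2) for ALT and (6, 1.2) for AST, both below the bilirubin line, although all the laboratory limits are met together on day 22. In D, any ALP of 2 or more gives the same result. E depends on a pairing rule that neither the protocol nor the SAP table states.

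**Size.** One misclassified participant is 1/3 = 33% in a cohort of 3. In the overall column, with the 19 participants treated by 06 May 2021 (protocol synopsis), it is 1/19 = 5.3%.

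**The case against.** The strongest reply is that SAP 15.4 was never meant to reproduce DLT criterion 2. It uses the safety set and a window to last dose + 30 days, whereas DLTs use the dose-escalation set and end with chemoradiotherapy. The condition of no other cause is a clinical judgement that cannot be programmed. Some difference between a laboratory table and the DLT result is therefore expected. This stands, and it is why the label is the main fault.

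A reader might infer that the primary endpoint or dose escalation is at risk. The documents do not support that. SAP 15.1 tabulates DLTs as decided by the SMC from the adverse event page, and the SMC analyses have their own plan.

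A reader might also infer that a lagged case such as C would be lost. It would not: the table counts it, and the listing shows every value, including ALP. The separate AST plot would also flag it if AST peaked later, above 3 × ULN, when bilirubin exceeded 2 × ULN.

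Nor does the protocol require the two values to coincide, so the timing conflict is chiefly between the two SAP outputs. The differences between > and ≥ matter only at exact equality. The 33% is what any single event amounts to in a cohort of 3.

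What remains is that a planned count and a planned flag are named Hy's Law without a condition that the protocol attaches to that name. A listing lets a reader find the error but does not correct the label.

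**Conclusion.** The point holds as a fault in descriptive safety outputs. Followed exactly, the SAP can count and flag a cholestatic participant as Hy's Law. It can also leave a participant who meets the protocol's laboratory limits unflagged on a plot while counting that participant in the table. The missing ALP limit is the most material difference, the peak-only bilirubin comes next, and the boundary differences are minor.

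The size is one participant at a time: 33 percentage points in a cohort of 3 and about 5 points overall with 19 treated. The documents give no liver results, so the number actually affected is unknown and may be zero. The conclusion rests on the written rules. The profiles only show that the disagreements are possible under weekly sampling and the stated entry limits. The DLT count is unaffected, and nothing here judges the clinical DLT rule.

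**What to change.** Reconcile SAP 15.4 with protocol 6.6.1, leaving the DLT rule as it is:

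1. Rename the present table row as potential Hy's Law (biochemical screen), and state whether it may pair values from different on-treatment samples.
2. Add a row for participants meeting the laboratory criteria of protocol 6.6.1: aminotransferase > 3, bilirubin ≥ 2 and ALP < 2 × ULN on the same sample. State that same-sample pairing is an analysis convention, since the protocol gives no interval. Footnote that exclusion of other causes remains a clinical judgement, and that the row need not equal the DLT count because the analysis set and window differ.
3. On the eDISH plots, use the cut-offs of the new row, call the upper right corner potential Hy's law, mark ALP status on each point, and flag anyone who meets the new row at any on-treatment sample, not only at the aminotransferase peak.

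A plot of peak aminotransferase against peak bilirubin would not by itself solve this. Profile E would land at (4, 2.3), inside the corner, from values 28 days apart. If such a plot is used, it should be presented as a screen, without calling its corner confirmed cases.

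The cost is SAP wording and minor programming. All four analytes are already collected (protocol Appendix 8).
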